8.4.2. Early Termination from the Study

For participants who are terminated from the study early, if possible, an Early Termination Visit should be conducted as described in [Table 2](#) or [Table 4](#). The participant will be permanently discontinued both from the IP and from the study at that time.

If the participant withdraws consent for disclosure of future information, the sponsor will retain and continue to use any data collected before such a withdrawal of consent.

If a participant withdraws from the study, he/she may request destruction of any samples taken and not tested, and the investigator must document this in the site study records.

8.4.3. Loss to Follow Up

A participant will be deemed lost to follow up after 3 attempts to contact the participant have been unsuccessful.

8.4.4. Replacement of Participants

Participants who discontinue or withdraw from the study will not be replaced. However, additional participants may be dosed if the early discontinuation rate is higher than expected.

9. TREATMENT OF PARTICIPANTS

9.1. Description of Investigational Product

SAGE-718 Oral Tablets are immediate release, white to off-white, round tablets containing 0.5 mg of SAGE-718 Drug Substance.

9.2. Prior Medications, Concomitant Medications, Restrictions, and Contraception Requirements

9.2.1. Prior and Concomitant Medications and/or Supplements

To be eligible to participate in this study, any concomitant medications must have been taken at a stable dose and frequency for at least 4 weeks before the first IP administration and be expected to continue at that stable dose until the final study visit is complete.

The start and end dates, route, dose/units, frequency, and indication for all relevant medications and/or supplements will be recorded at Screening, to include all medications and supplements taken within 60 days and all medications used to treat PD regardless of timing. At visits subsequent to Screening, all changes to any medication should be captured. All medications and/or supplements taken from the first dose of IP through the final study visit (including start and end dates, route, dose/units, frequency, and indication) will be recorded on the eCRF.

Because this study aims to measure effects on [REDACTED], it is important to evaluate single or combined concomitant medications and their doses for their potential effects on cognition. Investigators will carefully review concomitant medications for possible [REDACTED] [REDACTED] at Screening to determine participant eligibility and throughout the study.

9.2.2. Prohibited Medications

Treatment with an investigational drug or device is prohibited within the 30 days (or 5 half-lives of the IP, whichever is longer) prior to Screening and until the final Follow-up Visit.

During the course of the study, adjustment of medication or addition of medications that are known to affect cognitive performance (eg, stimulants, benzodiazepines, antipsychotics, anticholinergics) is to be avoided as much as possible. Any medication determined necessary for the welfare of the participant may be given at the discretion of the investigator at any time during the study, however, the use of any prohibited medications will be captured as a protocol deviation.

Use of the following medications is prohibited during the entire course of the study:

- Medications with potent effects at the NMDA receptor, including memantine, amantadine, ketamine, or related compounds
- Medications that inhibit cholesterol absorption (eg, ezetimibe)
- Bile acid sequestrants (eg, colestevlam, cholestyramine)
- Other medications given at doses, frequencies, or in combinations that are likely, in the opinion of the investigator, to have a deleterious effect on cognitive performance, based on the 2019 American Geriatrics Society Updated Beers[®] Criteria for

Potentially Inappropriate Medication Use in Older Adults ([American Geriatrics Society 2019](#))

- Prescribed cannabis or other THC-containing substances

9.2.3. Other Restrictions

Participants must agree not to use alcohol or any drugs of abuse (including marijuana) during the study.

9.2.4. Acceptable Forms of Contraception

Acceptable forms of highly effective contraception for participants of childbearing potential or for partners of male participants who are of childbearing potential include:

- Combined (estrogen and progestogen containing) oral, intravaginal, or transdermal hormonal contraception associated with inhibition of ovulation
- Oral, injectable, or implantable progestogen-only hormonal contraception associated with inhibition of ovulation
- Intrauterine device
- Intrauterine hormone-releasing system
- Bilateral tubal ligation or bilateral tubal occlusion (performed at least 3 months prior to Screening)
- Vasectomized partner (performed at least 3 months prior to Screening)
- Sexual abstinence (no sexual intercourse)

Acceptable forms of contraception for male participants include:

- Sexual abstinence (no sexual intercourse)
- History of vasectomy (performed at least 3 months prior to Screening)
- Condom with spermicide used together with highly effective female contraceptive methods if the female partner(s) is of childbearing potential (see above for list of acceptable female contraceptive methods)

9.3. Intervention after the End of the Study

Not applicable.

9.4. Treatment Adherence

The investigator(s) or designated staff will observe the participant taking the first dose of IP to identify any potential risks to adherence (such as difficulty opening the packaging or swallowing the tablets). The time and dose of IP administration will be noted in the source documents. The clinician will provide instructions for self-administration of the IP and train the participant to track adherence to the IP regimen and food intake in a participant diary. At clinic visits during the Treatment Period, a supply of IP will be dispensed for participants to take at home once daily until the next scheduled visit. Participants will be required to bring all components of the IP

packaging, including empty bottles and unused medication, and the participant diary to the clinic at every visit.

Adherence to the dosing regimen will be assessed at each in-clinic visit. Adherence will be assessed by reviewing the participant diary, examining the used packaging, and counting any tablets returned by the participant. This information will be documented in the source files and eCRF, along with any deviations from the prescribed dosage regimen. Details about IP accountability are included in Section [10.6](#).

9.5. Randomization and Blinding

This is an open-label study, in which all participants will received unblinded IP.

10. INVESTIGATIONAL PRODUCT MATERIALS AND MANAGEMENT

10.1. Investigational Product

SAGE-718 Oral Tablets are immediate release, white to off-white, round tablets containing 0.5 mg of SAGE-718 Drug Substance. The tablets are composed of SAGE-718 Drug Substance, mannitol, microcrystalline cellulose, sodium starch glycolate, and sodium stearyl fumarate.

10.2. Investigational Product Packaging and Labeling

SAGE-718 Oral Tablets are packaged in high density polyethylene bottles with desiccant, induction seal, and child-resistant closures.

The composition and pharmaceutical quality of the oral tablet will be maintained according to current Good Manufacturing Practice (GMP). Labels with all required information and conforming to all applicable Code of Federal Regulations and GMP/Good Clinical Practice (GCP) guidelines and all other applicable regulations will be prepared by Sage Therapeutics. The site pharmacist or designee will prepare labels for individual doses.

10.3. Investigational Product Storage

SAGE-718 Oral Tablets should be stored in the supplied bottles with 1 g desiccant, capped with a child-resistant closure and induction seal, and stored at room temperature. Refer to the shipping documentation for product expiry information.

10.4. Investigational Product Preparation

The IP will be provided to the site in tablet form and will be administered orally as described below.

10.5. Investigational Product Administration

Each 3.0-mg dose of IP will be self-administered as 6 tablets containing 0.5 mg of SAGE-718, once daily in the morning within 1 hour after initiating a meal containing approximately 30 g of fat. Participants are to swallow the tablets whole with approximately 240 mL (8 fluid ounces) of water. For doses taken in the clinic, site staff will watch the participant self-administer the IP.

10.6. Investigational Product Accountability, Handling, and Disposal

Upon receipt of IP, the pharmacist will inspect the IP and complete and follow the instructions regarding receipt and storage in the SAGE-718 Investigator's Brochure and in the pharmacy manual. A copy of the shipping documentation will be kept in the study files. The IP provided is for use only as directed in this protocol.

The investigator or designee must keep a record of all IP received, used, and returned/discarded. If dispensing errors or discrepancies are discovered by site staff or sponsor's designee, the sponsor must be notified immediately.

Designated site staff will dispense the IP to participants at weekly clinic visits as outlined in the Schedules of Assessments ([Table 2](#) and [Table 4](#)).

In Part B, site staff will access the interactive response technology (IRT) at the Screening Visit to obtain a participant identification number for each participant. On Day 1, site staff will access the IRT to enroll the eligible participant. During IP-dispensing clinic visits, site staff will access the IRT to obtain the medication identification number for the IP to be dispensed to that participant. The medication ID number and the number of tablets dispensed must be recorded. After Day 1, the participant will return all empty packaging and unused IP to the site at each clinic visit during the dosing period, and the number of tablets returned by the participant must be recorded.

The investigator, pharmacist, or qualified designee is responsible for drug accountability, reconciliation, and record maintenance (ie, receipt, reconciliation, and final disposition records). Sage Therapeutics or designee will be permitted access to the study supplies at any time with appropriate notice during or after completion of the study to perform drug accountability reconciliation. At the end of the study, any unused IP will be returned to Sage Therapeutics for destruction or destroyed locally per standard operating procedures at the site; disposition of IP will be documented.

More detailed information can be found in the SAGE-718 Investigator's Brochure and in the pharmacy manual.

10.7. Product Complaints

A product complaint is any written, electronic, or verbal expression of dissatisfaction regarding the identity, quality, reliability, safety, purity, potency, effectiveness, or performance (applicable for approved marketed products) of a drug product after it is released for distribution.

In the course of conduct of the study, study personnel may become aware of a product complaint associated with the use of a Sage product. Personnel shall notify Sage within 24 hours by forwarding the product complaint information via the contact information listed in [Table 1](#). Where possible, personnel should segregate and retain any product, materials, or packaging associated with the product complaint until further instruction is provided by Sage or its designated representative(s).

[REDACTED]

[REDACTED]

[REDACTED]

[REDACTED]

[REDACTED]

[REDACTED]

[REDACTED]

[REDACTED]

[REDACTED]

[REDACTED]

[REDACTED]

[REDACTED]

[REDACTED]

[REDACTED]

[REDACTED]

[REDACTED]

[REDACTED]

[REDACTED]

[REDACTED]

[REDACTED]

[REDACTED]

[REDACTED]

[REDACTED]

[REDACTED]

[REDACTED]

[REDACTED]

[REDACTED]

[REDACTED] es

11.1.9. Daily Remote Assessments

Participants will complete daily assessments using a mobile device each morning during the Treatment Period within 1 hour after IP administration. At scheduled clinic visits, the task will be performed in the clinic under observation by study staff, otherwise the participant will perform this task remotely (at home). Daily reminders will be provided to complete these assessments ([REDACTED]).

11.2. Clinical Pharmacology Assessments

[REDACTED]

11.2.1.1. Blood Sample Collection

Plasma samples for [REDACTED] will be collected according to the sampling collection times specified in Table 2, [REDACTED] Table 4, and [REDACTED]. The start day of IP administration is Day 1, and all postdose sampling times are relative to this time.

An additional [REDACTED] may be collected at any time if clinically indicated and at the discretion of the investigator (eg, for unusual or severe AEs).

Each sample will be marked with unique identifiers with at least the study number, participant number, and the nominal sample time. The date and actual time that the blood sample was taken will be recorded on the case report form. Samples will be shipped according to the instructions in the laboratory manual.

[REDACTED]
[REDACTED]

11.2.2. Pharmacodynamic Assessments

Blood samples will be collected, stored, and analyzed to identify [REDACTED] [REDACTED] associated with SAGE-718 pharmacodynamic characteristics. The samples and the results of the analyses may be used to help design future clinical studies, develop compounds, or develop assays and diagnostic or other tests. The sponsor will store the deidentified samples in a secure storage space with adequate measures to protect participant confidentiality. Only the sponsor and those persons or entities working with the sponsor will have access to the samples and associated data.

[REDACTED]
[REDACTED]
[REDACTED]
[REDACTED]
[REDACTED]
[REDACTED]

[REDACTED]
[REDACTED]
[REDACTED]
[REDACTED]
[REDACTED]
[REDACTED]
[REDACTED]
[REDACTED]
[REDACTED]

[REDACTED]
[REDACTED]

12. SAFETY ASSESSMENTS

12.1. Safety Parameters

All assessments will be conducted according to the Schedules of Assessments (Table 2 and Table 4) and the [REDACTED]

Abnormalities in physical examinations, vital signs, electrocardiograms (ECGs), and out of range values in laboratory test results will be interpreted by an investigator as clinically significant or not clinically significant in the source documents.

Information regarding diagnosis, isolation, and/or hospitalization due to COVID-19 will be documented as part of medical history, AE collection, and prior/concomitant medication/procedure collection throughout the study. Questions to be asked are as follows:

- Were you diagnosed with COVID-19 by a healthcare professional?
 - If the answer is “no”, no further questions.
 - If the answer is “yes”, the following questions are asked:
 - Did you have a test? If yes, was the result positive, negative or inconclusive?
 - Were you isolated? If yes, what were the dates of isolation?
 - Were you hospitalized? If yes, what were the dates of hospitalization?

12.1.1. Demography and Medical History

Demographic characteristics (age, race, sex, ethnicity) and a full medical history will be documented.

12.1.1.1. Screening Assessments

The following assessments will be performed only at Screening to confirm participant eligibility:

- Hoehn and Yahr Staging Scale (Goetz 2004): a scale used by clinicians to categorize the degree of progression of PD in an individual
- Test of Premorbid Functioning (Wechsler 2009): a language-based neuropsychological tool administered to participants in order to determine their level of intellectual function prior to the onset of cognitive impairment

12.1.2. Weight and Height

Height and weight will be measured and documented. Body mass index will be calculated and documented.

12.1.3. Physical Examination

Whenever possible, the same individual should perform all physical examinations. A full physical examination will be performed at Screening, to include assessment of body systems (eg, head, eye, ear, nose and throat; heart; lungs; abdomen; and extremities) as well as [REDACTED]. Thereafter, abbreviated physical examinations will

include assessment of general appearance, cardiovascular, respiratory, gastrointestinal, and neurological systems, followed by a targeted physical examination as needed. Unscheduled, symptom-directed physical examinations may also be conducted at the investigator's discretion.

12.1.4. Vital Signs

Vital signs comprise heart rate, respiratory rate, temperature, and blood pressure. Systolic and diastolic blood pressure are to be measured after the participant has been supine for at least 5 minutes prior to the measurement. Orthostatic blood pressure and heart rate will also be measured after the participant has been in the supine position for at least 5 minutes and then repeated approximately 1 and 3 minutes after standing.

12.1.5. Electrocardiogram

A 12-lead ECG will be performed at the time points described in [Table 2](#). At each time point, the ECGs will be recorded in triplicate at 1-minute intervals. The standard intervals (heart rate, PR, QRS, QT, and QTcF) as well as any rhythm abnormalities will be recorded.

Electrocardiograms will be performed after the participant has been resting in a supine position for at least 5 minutes. When ECG measurements coincide with safety assessments, vital signs assessment or blood draws, procedures should be carried out in said order (vital signs, ECG, blood draw).

12.1.6. Electroencephalogram

During Screening, EEG monitoring using the 10 to 20 international system for EEG electrode placement will occur for a duration of 1 hour. The assessment may be performed on any single day during the Screening Period, at any time of day, but preferably while the participant is in a fed state. If clinical events suspicious for seizure occur after Screening (eg, episodes of altered consciousness and/or involuntary motor behaviors), an unscheduled 1-hour EEG will be performed for safety. An additional 1-hour EEG may be performed at the discretion of the investigator to follow up on results from any unscheduled EEG. The EEG recording will be reviewed by an independent epileptologist to identify evidence of seizure risk (eg, spikes or spike and wave discharges), subclinical seizure (eg, synchronous sharp waves and/or synchronous spike and wave discharges), seizure corresponding to a clinical event, or changes consistent with a postseizure state (eg, focal slowing and/or diffuse slowing). Should the independent epileptologist identify evidence for a subclinical or clinical seizure, dosing with SAGE-718 will be stopped for that participant. All EEG abnormalities suggestive of seizure risk or postseizure state will be reviewed by the study medical monitor.

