 - e A full physical examination is to be conducted during Screening. Thereafter, physical examinations will include a brief assessment of general appearance, cardiovascular, respiratory, gastrointestinal, and neurological systems and followed by a targeted physical assessment as needed. A symptom-directed examination may be conducted at any time at the discretion of the investigator.
 - f An EEG will be performed for all participants at any time of day during Screening, preferably in a fed state. Subsequently, if the investigator or study staff become aware of events suspicious for seizure, an unscheduled 1-hour EEG will be performed for that participant. A second, follow-up, 1-hour EEG may be performed at the discretion of the investigator.
 - g ECG will be measured after the participant has been in the supine position for at least 5 minutes.
 - h “Baseline/Screening” C-SSRS form at Screening and “Since Last Visit” C-SSRS form thereafter.
 - i Samples for clinical laboratory assessments, detailed in Table 6, are to be collected ≤2 hours prior to dosing during the Treatment Period, and any time of day at other time points. Participants are to be in a fasted state for screening assessments only.
 - j Alcohol testing will be performed in the clinic, either by urine dipstick or breathalyzer.
 - k To confirm self-reported postmenopausal status in women only.
 - l Serum pregnancy tests for all female participants at Screening; urine pregnancy tests will be conducted for all female participants who are not postmenopausal or surgically sterile at other scheduled time points.
 - m To include testing for hepatitis B and C, HIV 1, and HIV 2

[REDACTED]

- o Participants and study partners will be trained to use all study-related software and devices. Additional guidance will be provided on choosing a meal with approximately 30 g of fat.

[REDACTED]

t Daily reminders will be sent to participants via a mobile device to complete assessments of [REDACTED] (see Section 11.1) within 1 hour following IP administration either remotely (at home) or in the clinic under observation by the study staff.

[REDACTED]

- v On visit days during the Treatment Period, participants will self-administer IP in the clinic under the supervision of study staff after the predose assessments and consumption of a morning meal.
- w Study staff will dispense sufficient IP for daily dosing at home until the next scheduled visit.

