7.4. Dose Adjustment Criteria

Dosing may be interrupted in an individual participant due to an AE considered by the investigator to be related to IP, however, no individual dose reductions will be permitted.

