7.4.1. Stopping Criteria

If clinical events suspicious for seizure occur after Screening, an unscheduled electroencephalogram (EEG) will be performed for review by an independent epileptologist to identify evidence of seizure activity (see Section 12.1.6). Should the independent epileptologist identify evidence for a subclinical or clinical seizure, dosing with SAGE-718 will be stopped for that participant.

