8.4. Investigational Product Discontinuation and Early Termination from the Study

A participant may withdraw from the study at any time at his/her own request for any reason. The investigator may discontinue a participant from the study and/or from IP for safety, behavioral, compliance, or administrative reasons.

The reason for IP discontinuation and/or the reason for early termination from the study must be documented in the participant's study record and recorded in the participant's electronic case report form (eCRF).

The investigator must notify the sponsor and/or the medical monitor when a participant stops participation in the study for any reason.

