12.2.3. Relationship to Investigational Product

The investigator must make the determination of relationship to the IP for each AE (not related, related). The following definitions should be considered when evaluating the relationship of AEs and SAEs to the IP.

Not Related	An AE will be considered "not related" to the use of the IP if there is not a reasonable possibility that the event has been caused by the IP. Factors pointing towards this assessment include but are not limited to: the lack of temporal relationship between administration of the IP and the event, the presence of biologically implausible relationship between the product and the AE, or the presence of a more likely alternative explanation for the AE.
Related	An AE will be considered "related" to the use of the IP if there is a reasonable possibility that the event may have been caused by the product under investigation. Factors that point towards this assessment include but are not limited to: a positive rechallenge, a reasonable temporal sequence between administration of the drug and the event, a known response pattern of the suspected drug, improvement following discontinuation or dose reduction, a biologically plausible relationship between the drug and the AE, or a lack of alternative explanation for the AE.

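### The mandatory seizure stop rests only on the epileptologist's EEG finding, with no deadline for the EEG or its read, no required hold meanwhile, and no required stop if the EEG misses a clinical seizure

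*Protocol*

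**What the plan says.** Protocol Section 7.4.1 (Stopping Criteria) starts the process: "If clinical events suspicious for seizure occur after Screening, an unscheduled electroencephalogram (EEG) will be performed for review by an independent epileptologist". Section 12.1.6 repeats this, fixes the recording at 1 hour, and gives the consequence: "Should the independent epileptologist identify evidence for a subclinical or clinical seizure, dosing with SAGE-718 will be stopped for that participant". Footnote f to the Part A schedule (Table 2), repeated in the Part B schedule (Table 4), ties the trigger to site awareness: "Subsequently, if the investigator or study staff become aware of events suspicious for seizure, an unscheduled 1-hour EEG will be performed for that participant". SAP 16.7 restates the trigger and says only that EEG data will be listed.

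Two further steps in 12.1.6 follow the read. A repeat EEG is optional: "An additional 1-hour EEG may be performed at the discretion of the investigator to follow up on results from any unscheduled EEG". Lesser findings go to oversight: "All EEG abnormalities suggestive of seizure risk or postseizure state will be reviewed by the study medical monitor". Neither carries a dosing action.

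Other provisions let someone act sooner:

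- Section 7.4: "Dosing may be interrupted in an individual participant due to an AE considered by the investigator to be related to IP". The relatedness threshold in 12.2.3 is low: an event counts as related "if there is a reasonable possibility that the event may have been caused by the product under investigation".
- Section 8.4: "The investigator may discontinue a participant from the study and/or from IP for safety, behavioral, compliance, or administrative reasons". This needs neither an EEG nor a relatedness judgement.
- Section 7.5 lets the sponsor terminate the study, or any portion of it, for safety.
- Section 12.2.2 gives convulsions at home as an example of a medically important SAE, and 12.2.5 requires notice to the sponsor within 24 hours.

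**The concern.** Seizure is the only criterion in Section 7.4.1, so the rule should protect a participant from the moment a seizure is suspected. As written, the mandatory part takes effect only once an EEG recorded after the event has been read and found positive. Dosing is daily and mostly at home, from a supply that lasts until the next visit (7.1.3, 9.4), so unless someone intervenes the tablets continue.

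Two situations are left to discretion. One is the wait between the site learning of a suspicious event and the completed read. The other is a clinically evident seizure followed by a non-diagnostic EEG, where no stop is required at any time. At stake is the further exposure of the affected participant, and consistency across approximately 10 sites. TEAE incidence, the primary endpoint, is not at stake, because such events are recorded and tabulated either way.

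**Working it through.** The documents state no figure for this rule, so there is none to reproduce. The check is a reading of the provisions, followed by simple dose counts.

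**Step 1: what each provision requires.**

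| Provision | Deadline for EEG or read | Required hold | Required stop |
|---|---|---|---|
| 7.4.1 and 12.1.6 | None | None | Only on the epileptologist's finding of a subclinical or clinical seizure |
| Footnote f (Tables 2 and 4) | None | None | None |
| SAP 16.7 | None | None | None |
| 7.4 | Not applicable | Permitted, if judged related | None |
| 8.4 | Not applicable | Not addressed | Permitted |
| 7.5 | Not applicable | Not addressed | Permitted, for the study or a portion of it |
| 12.2.5 | 24 hours, for SAE notice only | None | None |

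**Step 2: the non-diagnostic EEG.** Section 12.1.6 lists four kinds of finding: seizure risk, subclinical seizure, seizure matching a clinical event, and postseizure change. It attaches the stop to subclinical or clinical seizure and sends risk and postseizure findings to the medical monitor. A witnessed convulsion followed by a normal recording therefore triggers neither the stop nor the monitor's review. The text does not settle whether postseizure slowing counts as evidence for a clinical seizure.

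**Step 3: doses exposed by the gap.** Inputs: one dose daily for 14 days (Part A) or 28 days (Part B), Section 7.3.

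- Each day of waiting: 1/14 = 7.1% of the Part A course; 1/28 = 3.6% of Part B.
- Doses left after an event that follows the Day d dose: 14 − d or 28 − d. The largest values, at d = 1, are 13 and 27; the smallest is 0. Doses taken before the site knows of the event are in this count, although no rule could prevent them.
- Read time is not in the documents. At an assumed 1 to 7 days, the wait covers 1 to 7 doses, if that many remain. That range is an illustration, not a bound.

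No average is given, because it would require an assumed distribution of the event day.

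**Step 4: cost of a hold that ends in resumption.** SAP 13.9.1 plans 6 tablets a day, 84 in Part A and 168 in Part B, and reports adherence with a category below 80%.

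- Part A: 2 days, (84 − 12)/84 = 85.7%; 3 days, (84 − 18)/84 = 78.6%.
- Part B: 5 days, (168 − 30)/168 = 82.1%; 6 days, (168 − 36)/168 = 78.6%.
- A hold that becomes a stop by Day 14 does not lower adherence, because planned tablets are then the last dose day × 6. With a last dose on Day 6, this is 36/36 = 100%.
- Planned doses in all: 11 × 14 + 22 × 28 = 154 + 616 = 770. If there were 1 to 10 false alarms at 2 days each (both assumed), the loss is 2 to 20 doses, or 0.3% to 2.6%.

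**The case against.** The strongest reply is that the gap harms a participant only if a study physician keeps dosing after a suspected or evident seizure. The sections do not direct that dosing continue; they are silent until the read. Sections 7.4 and 8.4 already let the investigator hold or stop, and the sponsor, told of an SAE within 24 hours, can act under 7.5. Events should also be uncommon. Section 8.2 excludes a history of seizures or epilepsy (apart from a single childhood febrile episode), brain surgery, significant head injury and intracranial abnormality. Every participant has a screening EEG, and Section 5 reports no SAEs or discontinuations due to AEs in earlier clinical studies. A compulsory hold has its own cost: the trigger examples include involuntary motor behaviors, in a Parkinson's disease population.

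Most of this stands, and it limits the size of the point. It does not remove the gap, because every one of those powers is optional and none sets a time. The exclusions and the screening EEG make an event less likely but do not say what to do when one occurs.

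A reader might infer more than the documents support. They do not show that the investigator lacks power to hold dosing, since 8.4 needs no EEG and no relatedness finding. They do not show that 13 or 27 further doses are to be expected: those are the most that could remain, and the excess is zero if anyone acts. Nor do they show any distortion of the primary endpoint.

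**Conclusion.** The concern holds as a gap in a safety rule. The only mandatory participant-level stop depends on a positive EEG read. No time limit or required hold covers the wait, and a clinical seizure that the EEG misses requires no stop. Followed exactly, the mandatory rule lets daily dosing continue in the situation it was written for unless the investigator or sponsor chooses to intervene.

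The size is one dose per day of waiting, and at most 13 (Part A) or 27 (Part B) doses after an on-treatment event. How often such events would occur, and how long a read takes, cannot be derived from the documents. A turnaround time in a separate manual cannot be ruled out, but neither document refers to one for the EEG, and a dosing hold belongs in the protocol. No analysis or endpoint changes.

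**What to change.** In Sections 7.4.1 and 12.1.6, with a cross-reference in 7.4, state:

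> When the site becomes aware of an event that triggers the unscheduled EEG, dosing is held until the EEG is read, whether or not the AE is judged related. The EEG is to be done and read as soon as possible (target 2 days). If it is late or not done, the hold continues until the investigator and medical monitor decide. Dosing is stopped if the epileptologist finds evidence of a subclinical or clinical seizure, or if the investigator judges that a clinical seizure occurred, even if the EEG is non-diagnostic. Otherwise dosing may resume at the investigator's discretion, after medical monitor review of any seizure-risk or postseizure abnormality. Sections 7.4 and 8.4 still apply.

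The 2 days is a proposal, not a figure from the documents, and has to be agreed with the sites and the epileptologist. No new procedure, reader or SAP table is needed.

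The downside is about one missed dose per day of hold for events that prove not to be seizures; their number is unknown. With resumption, a hold of 3 or more days in Part A, or 6 or more in Part B, puts a participant in the below-80% adherence category, which is descriptive only. The second stop condition still rests on investigator judgement, so some variation between sites remains. What it adds over 8.4 is that, once a clinical seizure is judged to have occurred, stopping is required.
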